7.4. Exploratory endpoints

To demonstrate the efficacy of RT001 on change from baseline at 11 months in clinical symptoms as measured by:

- 1. Modified Friedreich's Ataxia Scale (mFARS)
- 2. Fatigue Symptom Scale (items 2. 4. 7.9 of the total fatigue scale)
- 3. Clinician-rated Clinical Global Impression of Change (CGI-C)
- 4. Activities of daily living (ADL) elements of fatigue scale (items 5,6, 8, 10, and 11)
- 5. Patient Global Impression of Change (PGI-C)
- To evaluate the effects of RT001 on Visual Analogue Scale [VAS]
- To evaluate the effects of RT001 on speech measurements and Speech Assessment questionnaire
- To evaluate the effect of RT001 on T25FW
- To evaluate the effects of RT001 on FARS-Neuro
- To evaluate the effects of RT001 on FARS-ADL.

- To evaluate the effects of RT001 on SF-36
- To evaluate the effects of RT001 on the Neuro-QoL scales (Upper Extremity Function and Lower Extremity Function)
- To evaluate the effects of RT001 on the frequency of falls as reported in a fall diary and subject's fear of falling
- To evaluate the effects of RT001 on the Patient Global Impression of Change (PGI-C) Scale
- To evaluate the effects of RT001 on efficacy assessments after 4 months of treatment
- To evaluate the effects of RT001 on efficacy assessments after 8 months of treatment
- To evaluate the effects of RT001 on ejection fraction as reported in the Echocardiogram
- To evaluate the effects of RT001 on hypertrophy as reported in the Echocardiogram

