Subjects will perform CPET on a stationary recumbent bike at Screening, on Day 1, Day 120 (\pm 30 days), Day 240 (\pm 30 days), and Day 330 (\pm 30 days). Peak work rate and VO₂ MAX will be measured during incremental exercise testing. CPET should occur after fasting (if the subject has had a meal/snack) for a minimum of 2 hours, with neither caffeine nor nicotine for at least 12 hours before testing.

Subjects (with or without assistive device) will perform a T1MW and electronically measured T25FW at Screening, on Day 1, Day 120 (\pm 30 days), Day 240 (\pm 30 days), and Day 330 (\pm 30 days).

CPET and the T1MW/T25FW should be separated in time to allow the subject to recover sufficiently before doing the next test. All tests should be done at approximately the same time and order for each visit.

The FARS-Neuro and clinician-rated CGI scale will be performed at Screening, on Day 1, Day 120 (\pm 30 days), Day 240 (\pm 30 days), and Day 330 (\pm 30 days) by a qualified physician or health professional who is trained on the use of the tool. The CPET examination should always precede the FARS-Neuro evaluation at all visits.

A trained health professional will also work with the subject to perform the speech measurement recording at Screening, on Day 1, Day 240 (\pm 30 days), and Day 330 (\pm 30 days).

The FARS-ADL, SF-36, VAS (for Fatigue), Fatigue scale, Neuro-QoL scales (lower extremity function and upper extremity function) and Fall Questionnaire will be completed by the subjects at screening and at the visits on Day 1, Day 120 (\pm 30 days), Day 240 (\pm 30 days), and Day 330 (\pm 30 days). The PGI-C scale and VAS (for Improvement of FA symptoms) will be completed by all subjects at Day 120 (\pm 30 days), Day 240 (\pm 30 days), and Day 330 (\pm 30 days).

In between the clinic visits, subjects will also be contacted by phone by a study site staff member and asked questions relating to the PGI-C, Fatigue scale, Neuro-QoL Scales (lower extremity function and upper extremity function), and questions 8 and 9 of the fall questionnaire. These phone 'visits' will take place monthly. A Speech Assessment Questionnaire will be completed by the subject and parents/caregiver (as applicable) at Screening, on Day 1, Day 240 (\pm 30 days), and Day 330 (\pm 30 days).

Between clinic visits, subjects will be asked to keep a daily log (diary) documenting falls, nearfalls, stumbles, and fear of falling (Screening through Day 330).

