12.6.8. Fall Diary

The subjects will be asked to keep a daily log (diary) documenting falls, near-falls, stumbles, and fear of falling from screening until the end of treatment. Falls are defined as any event that results in unintentionally falling to the ground. Near-falls are defined as losing balance with no fall to the ground (e.g. hold on to something/somebody, or fall onto a chair, bed, or other soft landing). Stumbles are defined as losing balance momentarily with regaining of footing and no fall.

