12.7.7. Echocardiogram

Subjects will need to get an echocardiogram done at Screening if there has not been an echocardiogram obtained in the 12 months prior to screening. An echocardiogram obtained up to 12 months prior to Screening can be used for the assessment of the eligibility in the study. A repeat echocardiogram will be obtained on Day 330 (± 30 days).

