Change from baseline (CFB) will be analyzed by comparing the change between treatment groups using a mixed model with repeated measures (MMRM). The MMRM will compare the estimated change from baseline between treatments for the primary endpoint. This analysis will assess whether there is a difference in estimated CFB between active and placebo groups at 11 months.

The primary analysis will use the ITT methodology and an MMRM methodology with a random slope and intercept for each individual. Due to the small sample size the model will be optimized by implementation of two risk scores (baseline and slope) that account for multiple baseline covariates in one variable. The risk scores will be derived from blinded data using the GST change from baseline values and generated using the baseline model covariates (excluding treatment and visit; baseline risk score) or the baseline model covariates*time interactions (slope risk score). The risk scores will be included as covariates in the model.

To calculate the baseline risk score, the GST change score is regressed on the covariates listed below. Individual coefficients for the baseline risk score are multiplied by individual covariate values and summed. A separate slope risk score is calculated for baseline covariates interacting with time.

The MMRM with primary outcome CFB value as the response variable will include the following covariates and fixed effects:

- baseline risk score:
 - baseline score for GST
 - age
- slope risk score:
 - baseline score for GST * time
 - age*time
- Time (continuous)
- Time by treatment interaction (time*treatment)
- baseline score for parameter of interest (if not in GST)
- site pooled by region (random effect)

Model assumptions will be evaluated. If the parametric assumptions are evaluated as inappropriate or violated, rank analogues will be advanced.

All secondary and exploratory endpoints CFB values will be analyzed using the MMRM described above. This analysis will assess whether or not there is a difference in estimated CFB values between treatment group and placebo at the 11-month model estimate using least squares means estimates from the MMRM model.

Speech measurement reporting will be analyzed by a third party vendor. A separate report will be provided.

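### The single random-slope change model cannot be fitted as specified to the one-visit echocardiography endpoints and suits the fall-diary counts poorly; both exploratory endpoints need their own model

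*Combined protocol and SAP*

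**What the plan says.** Section 14.1 sets out one mixed model and then extends it: "All secondary and exploratory endpoints CFB values will be analyzed using the MMRM described above". The model described is an "MMRM methodology with a random slope and intercept for each individual". Time is continuous, and the only treatment term listed is "Time by treatment interaction (time*treatment"); there is no treatment main effect. The covariates include "baseline score for parameter of interest (if not in GST"). Neither falls nor echocardiography is a GST component, so each would be adjusted for its own baseline. If parametric assumptions fail, rank versions are used. Speech recordings go to an outside vendor. Full details are deferred to a separate statistical analysis plan.

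Section 7.4 lists among the exploratory aims "To evaluate the effects of RT001 on the frequency of falls as reported in a fall diary", and also ejection fraction and hypertrophy on echocardiogram. For the latter, section 12.7.7 provides a baseline and a single follow-up: "A repeat echocardiogram will be obtained on Day 330" (± 30 days).

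The diary period is given in two ways. Section 8.1 has "fear of falling (Screening through Day 330"), while section 12.6.8 has "fear of falling from screening until the end of treatment". Section 8.1 puts the last dose 4 weeks after the Day 330 visit.

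**The concern.** A random-intercept-and-slope model needs repeated post-baseline values on each subject. Echocardiography supplies one. A fitting routine will then fail to converge or return an arbitrary split of the variance, and the analyst will have to change the model after the fact.

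Fall frequency raises a different problem. It is a count, probably over-dispersed, collected over diary intervals of different lengths. No count model or exposure term is named, and it is not stated whether frequency means a count or a rate. The slope form also assumes that the treatment difference is zero at the start and grows in a straight line. If the drug changes the fall rate early and by a constant ratio, that form uses the early months badly.

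At stake are the readability and sensitivity of some exploratory results, and an avoidable deviation from the plan. The primary analysis is not involved.

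**Working it through.** **The plan's own power figure.** The only one is for peak workload (section 14.2): 30 per arm, difference 15.8, SD 11.1, two-sided alpha 0.05. The noncentrality is 15.8 / (11.1 × √(2/30)) = 5.51, which gives power 0.9997 and reproduces the stated figure of over 99%. Nothing comparable is given for falls or echocardiography.

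**Echocardiography.** With one value per subject at time t, the model implies

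Var(change) = σ²(intercept) + 2t·σ(intercept, slope) + t²·σ²(slope) + σ²(residual).

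That is four parameters and one variance to estimate them from. The intercept and residual variances enter only as a sum, so no data of this shape can separate them. In a simulated data set the REML log-likelihood was −106.4037 for intercept/residual splits of 0/16, 8/8 and 15.9/0.1. It differed by at most 0.21 for any slope split tried. Ranking the values does not help, because there is still one per subject.

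The treatment effect survives. At a single nominal visit, time × treatment is simply 11 times the treatment indicator. Across the variance splits the Month 11 estimate moved only from −0.63 to −0.82, with SE 0.97 to 1.05. An ANCOVA without subject effects gave about the same answer.

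**Falls: intervals.** The pre-dose diary runs at most 30 days (14 to 30 under section 13.1). The nominal length from Day 240 to Day 330 is 90 days. With the ± 30-day windows it can be anything from 300 − 270 = 30 to 360 − 210 = 150 days.

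**Falls: the short baseline.** With the endpoint's own baseline Y0 as a covariate,

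Y1 − Y0 = a + τ·treatment + b·Y0 + e is the same model as Y1 = a + τ·treatment + (b + 1)·Y0 + e.

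The estimate of τ is identical, so a noisy baseline is down-weighted and not subtracted in full. The simulation assumed 30 per arm, 330 days, 1, 2 or 4 falls per 30 days, gamma dispersion 0.5 to 2, a baseline of 14 or 30 days, and rate ratio 0.5. Power over that grid was:

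| Analysis | Power |
|---|---|
| Change, not adjusted for baseline | 0.20–0.65 |
| Change, baseline-adjusted | 0.58–0.96 |
| Rank ANCOVA | 0.43–0.94 |
| Negative binomial with offset (Wald) | 0.61–0.97 |

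The adjusted Gaussian analysis is within 1 to 8 points of the negative binomial. The latter is flattered, because its Wald test ran at 7 to 12% under the null.

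**Falls: the slope form.** The model forces the group difference at Months 4, 8 and 11 to be 4β, 8β and 11β. Under a constant rate ratio the difference is about the same at all three. At Month 4 the model therefore expects 4/11 = 36% of an effect that is already fully present. With a 30-day baseline, dispersion 1 and rate ratio 0.5 (risk scores and region omitted; Monte Carlo error about 3 to 4 points for the slope model):

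| Falls per 30 days | Planned slope model | Baseline-adjusted mean change | Negative binomial (Wald) |
|---|---|---|---|
| 1 | 0.56 | 0.77 | 0.81 |
| 2 | 0.65 | 0.87 | 0.88 |
| 4 | 0.77 | 0.94 | 0.95 |

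A less favourable setting used a 22-day baseline and rate ratio 0.6, again with assumed fall rates, and gave the negative binomial a permutation p-value. The slope model had 31–75% power, the baseline-adjusted rate 42–93% and the negative binomial 36–87%. Setting by setting, the gain over the slope model was about 10 to 20 points for the adjusted rate. It was about 5 to 16 points for the negative binomial, with none in one high-dispersion setting.

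**Zero baseline counts.** The negative binomial zero probability is (1 + μ/k)^(−k). Over 22 days at 1 fall per 30 days, μ = 22/30 = 0.733. That gives 61% for k = 0.7 and 55% for k = 1.5. At 2 falls per 30 days it is 45% and 36%. A plain log baseline rate would be undefined for about half the subjects, so the covariate needs an offset for zeros.

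**The case against.** Section 14.1 attaches the random slope and intercept to the primary analysis, so carrying them to echocardiography through the cross-reference is a reading. That is fair. But no other covariance structure is described, so the cross-reference has nothing else to point to.

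The section also defers full details to a separate plan to be finalised before unblinding, and it offers assumption checks with a rank fallback. That plan is not among the documents, so nobody can say that it lacks a count model. What can be said is that the text in hand prescribes one model and excepts neither falls nor echocardiography. The rank fallback does not repair a one-visit data set.

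A reader might infer that the short diary baseline and the Gaussian change score cost the fall analysis around half its power. The documents do not support this, because section 14.1 adjusts for the endpoint's own baseline and that recovers most of the loss. What remains comes mainly from the slope-only treatment term, and it depends on a constant rate ratio. If the effect built up steadily over time, the slope form would fit better and the gain would shrink or could reverse.

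On the diary end date, section 14.1 already confines efficacy analyses to the 11-month on-treatment period, so the effect on analysis is small. The two sections still disagree about how long subjects keep the diary. Section 13.8 collects it at Day 330, and section 13.10 lists no later collection.

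**Conclusion.** The point holds as a minor specification matter.

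- **Echocardiography.** The variance components are not identifiable from one post-baseline value; this follows from the visit schedule and needs no assumption. It would be too strong to say that no treatment effect can be estimated, since the Month 11 contrast is estimable and stable.
- **Falls.** A whole-period analysis is a better match to the data. The likely gain is about 10 to 20 points of power with a baseline-adjusted rate and about 5 to 16 with a permutation negative binomial, nil in one high-dispersion setting. These figures rest on assumed fall rates, dispersion and a constant rate ratio. The documents give none of these.
- **Diary period.** Sections 8.1 and 12.6.8 must be reconciled.

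All the endpoints concerned are exploratory, so the primary conclusion does not change.

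**What to change.** Amend section 14.1, or state in the separate plan before unblinding:

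- **Ejection fraction and hypertrophy:** ANCOVA of the Day 330 value on baseline and FARS stratum (≤45, >45), with no subject random effects.
- **Falls, near-falls and stumbles:** one analysis of the total count from Day 1 to Day 330. Use a negative binomial model with a log(diary days) offset, FARS stratum and a baseline covariate that tolerates zeros, such as log((count + 0.5)/days). Take the p-value by permutation within stratum, because the Wald test is too liberal at this sample size. A baseline-adjusted analysis of the follow-up rate performs about as well and is an acceptable alternative. Power does not favour the negative binomial over it; the case for the count model is direct handling of exposure and a result on the ratio scale.
- **Diary end date:** give one end date in sections 8.1 and 12.6.8.

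The cost is a few sentences and two standard models. Falls would then be reported as a rate ratio and not as a mean change.

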AUC _{0-12h}	ug h/mL	6	809	269	5	3400	459
AUC _{0-24h}	ug h/mL	6	1527	445	5	6800 ^a	918
AUC _{last} b	ug h/mL	6	3345	950	5	13854	2899
t _{1/2}	h	5	42.3	9.77	4	30.3	18.30

Medians shown for T_{max}, T_{min}

The CPET testing change between baseline and Day 28 showed an improvement in peak workload of +0.16 watts/kg (25.7%) in the subjects on all doses of study drug (n=10) vs. comparator (n=6). The reported p value in post hoc analysis was p=0.008 (Mann-Whitney Rank Sum test). This modified Intent-To-Treat (mITT) analysis excluded 2 subjects unable to either start or complete the test, and full Intent-To-Treat (ITT) analysis including the two subjects, had a p= 0.021. Similarly, the study showed a strong trend from baseline to Day 28 of therapy in peak oxygen consumption (VO₂ MAX). The median change from baseline for comparator vs. RT001 was -0.02 L/min vs. 0.14 L/min; respectively, p=0.116. Assessment on the neurological examination of the Friedreich Ataxia Rating Scale (FARS-Neuro) scoring showed a trend in improvement between baseline and Day 28 of treated vs. placebo patients (a decrease of 1.95 FARS points, p= 0.348 ITT). This result was on top of a decrease of 2.8 FARS points in the placebo group, (i.e. a 4.75 FARS point decrease from baseline for the treated group). highlighting the robust placebo effect in the FARS-Neuro measure that has been documented elsewhere (Zesiewicz, 2017). Expected change in FARS-Neuro for one month of dosing based on extensive natural history data (Patel et. al., 2016) would be $\sim +0.25$ FARS points. The average stride speed (stride time)⁻¹ during the T25FW, measured with an electronic motion sensor, improved 7% (p=0.15 ITT). Traditionally measured T25FW⁻¹ (via stopwatch) showed no signal of significance (p=0.88).

The relatively small size and short duration of the trial necessitates caution in over-interpretation of efficacy results. Nevertheless, clear correlations between the various parameters measured

a – For comparison of the two dosing regimens, the AUC_{0-24h} shown here is the AUC_{0-24h} at steady state (= $2 * AUC_{0-12}$) for the BID regimen

b – AUC_{last} was 72 h after the last dose in all subjects

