6.8. Potential Risks and Benefits to Human Subjects

FA is a rare, inherited recessive disorder characterized by progressive degenerative changes, in particular to mitochondria, which lead to morbidity and mortality at a young age. There is currently no approved therapy for this condition. RT001 offers a novel yet specific approach to mitigation of the harmful oxidative attack on lipids of mitochondrial membranes, which has potential benefit if the hypothesis is proven in this and subsequent efficacy studies. RT001 is based on a common, essential dietary sourced fatty acid, LA. The slight modification to the chemical structure of LA, the site-specific replacement of 2 hydrogen atoms with 2 deuterium atoms, does not impact any of the key properties and fate of the lipid, yet remains functionally active against unwanted, pathological oxidative attack. The deuterium presents low risk (see below) in that it is stably incorporated in covalent bonds, and the amount dosed is relatively low. Thus, the risk-benefit profile is thought to be favorable and suggests a future potential benefit of RT001 treatment in this intractable condition.

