Responder analyses will be run on MVO2 (primary), GST, T1MW, Peak Workload, mFARS, and CGI-C (functional assessment). Responder analyses are performed to illustrate the clinical meaningfulness of the relationship between treatment differences and efficacy outcomes on a per

person basis. Responder analyses will be assessed at change from baseline cutoffs at the overall quartiles for each of the three variables. Patients who die or are unable to perform the test during the study will be counted as non-responders. Patients who do not complete will be carried forward using the last observation carried forward and the imputed value at the study endpoint will be used for the responder analysis.

In addition to summarizing the results for each relationship between individual clinical responses and treatment multiple clinical responses will also be correlated with treatment using the five GST component outcomes individually. Those who experienced the following combined clinical responses will be summarized in terms of counts and percent:

• Improvement or stabilization on at least 1, 2, 3, 4, and all of the 5 responder endpoints.

The PK of D2-LA and H2-LA will be characterized in terms of minimum and maximum exposure at steady state, based on a validated assay. The PK of D2-LA and H2-LA in RBC, D2-ARA, and H2-ARA also will be characterized in terms of minimum and maximum exposure at steady state; the validation of the assays to characterize these concentration values has not yet been validated.

Full details of planned analyses will be provided in a separate statistical analysis plan.

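### LOCF in the responder analyses puts a Day 120 or Day 240 value in place of Month 11 for non-completers, and misstates response in a direction that depends on the arm's course

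*Combined protocol and SAP*

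**What the plan says.** Section 14.1 (Statistical Plan) plans responder analyses for MVO2, GST, T1MW, peak workload, mFARS and CGI-C. It gives two rules for subjects without a Month 11 result:

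- For death or inability, the rule is failure: "Patients who die or are unable to perform the test during the study will be counted as non-responders".
- For all other non-completers, the rule is LOCF: "Patients who do not complete will be carried forward using the last observation carried forward". The carried value then stands in for the Month 11 result when response is scored.

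Response is judged in two ways. For single endpoints: "Responder analyses will be assessed at change from baseline cutoffs at the overall quartiles for each of the three variables". For the combined summary: "Improvement or stabilization on at least 1, 2, 3, 4, and all of the 5 responder endpoints". No threshold for stabilization is stated.

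Section 13.13 (Early Termination Visit) lists safety procedures only: no exercise test, walk test, FARS or CGI. After baseline, the Schedule of Events places these efficacy tests at Day 120, Day 240 and Day 330.

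All change-from-baseline analyses in Section 14.1 use the mixed model. LOCF appears only in the responder analyses, and the document gives no sensitivity analysis for it. Section 14.1 describes the responder analyses as illustrating clinical meaningfulness.

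**The concern.** A subject who leaves after Day 120 is scored on a result about 7 months old (330 - 120 = 210 days). One who leaves after Day 240 is scored on a result about 3 months old (330 - 240 = 90 days). Carrying a value forward is harmless only if nothing would have changed in between, and the plan assumes change in both arms. Section 6.8 says of the disease: "FA is a rare, inherited recessive disorder characterized by progressive degenerative changes". The sample-size calculation has placebo falling and active rising.

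A carried value therefore misses later decline in one kind of subject and later gain in another. The responder tables are meant to show what the treatment difference means for individual patients, and with 30 subjects per arm a few misclassified subjects would show. Because the cutoffs are overall quartiles, carried values also enter the thresholds applied to everyone.

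**Working it through.** **Inputs from the document**
- Peak workload change: active +7.5, placebo -8.3, SD 11.1 in both groups, 30 per arm, two-sided alpha 0.05 (Section 14.2; minus sign on 8.3 as printed in the synopsis). Unit and time point are not stated.
- FARS-Neuro natural history: about 0.25 points of worsening per month (Section 6.4).

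**Assumptions**
- The means and SD apply at Month 11, and mean change is linear in time.
- SD at month m is constant, proportional to the square root of t, or proportional to t.
- Stable or improved means change of at least 0.
- Dropout is 10-30%, all after Month 4. The document gives no rate.

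**Plan's own figure.** Noncentrality = 15.8 / (11.1 x sqrt(2/30)) = 5.51. With 58 df, power is 99.97%, which agrees with the stated figure of over 99%. No responder rate is stated, so there is none to reproduce.

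**One dropout.** P(stable or improved at month m) = Phi(mu x (m/11) / SD_m).

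Placebo, Month 11: Phi(-8.3/11.1) = 22.7%. Placebo, Month 4: the mean is -8.3 x 4/11 = -3.02. Constant SD gives Phi(-3.02/11.1) = 39.3%. Square-root SD is 11.1 x sqrt(4/11) = 6.69, which gives 32.6%. SD proportional to t is 11.1 x 4/11 = 4.04, which gives 22.7%.

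| Value used | Constant SD | SD ~ sqrt(t) | SD ~ t |
|---|---|---|---|
| Declining (-8.3), Month 11 | 22.7% | 22.7% | 22.7% |
| Declining, Month 8 carried | 29.3% | 26.2% | 22.7% |
| Declining, Month 4 carried | 39.3% | 32.6% | 22.7% |
| Improving (+7.5), Month 11 | 75.0% | 75.0% | 75.0% |
| Improving, Month 8 carried | 68.8% | 71.8% | 75.0% |
| Improving, Month 4 carried | 59.7% | 65.8% | 75.0% |

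**Quartile cutoffs.** Suppose both arms decline at the placebo rate and the cutoffs stay at the Month 11 quartiles (-15.79, -8.30, -0.81). The true rates of 75/50/25% become, with Month 4 carried, 87.5/68.3/42.1% (constant SD), 97.2/78.5/37.1% (sqrt t) or 99.9/90.5/29.2% (t). Here the shift persists even where the zero threshold shows none. Movement of the cutoffs themselves is not quantified.

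**Whole arm, constant SD.** Rate = (1 - d) x Month 11 rate + d x Month 4 rate, with the same d in both arms.

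| d | Placebo | Active | Difference | Difference, all dropouts non-responders |
|---|---|---|---|---|
| 0 | 22.7% | 75.0% | 52.3 | 52.3 |
| 10% | 24.4% | 73.5% | 49.1 | 47.1 |
| 20% | 26.0% | 72.0% | 45.9 | 41.8 |
| 30% | 27.7% | 70.4% | 42.7 | 36.6 |

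The placebo shift of 1.7 to 5.0 points is 0.5 to 1.5 subjects in 30.

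**Unequal dropout, both arms declining equally.** With 20% (active) v 5% (placebo), LOCF adds (0.20 - 0.05) x (0.393 - 0.227) = +2.5 points for active. That is 0.75 of a subject in 30. With 30% v 10% it adds +3.3 points.

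**FARS-Neuro.** Expected worsening is 0.25 x 11 = 2.75 points at Month 11, 1.0 at Month 4 and 2.0 at Month 8. LOCF omits 1.75 or 0.75 points.

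**The case against.** The case for leaving the text alone has several parts.

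- **Role.** The analysis is illustrative, the primary inference uses the mixed model, and Section 14.1 defers full detail to a separate statistical analysis plan. This stands and limits the severity.
- **Inputs.** The -8.3, +7.5 and 11.1 are for peak workload only, without a time point, and six responder endpoints are listed. With SD proportional to t, the sign of change does not shift at all. This stands, so the percentages are illustrations and not predictions.
- **Protection already present.** Deaths and subjects unable to perform the test are non-responders, which covers the dropouts most closely tied to progression. This stands for those subjects. Other withdrawals remain.

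A reader might go further and infer any of three things.

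- **Leaving early is scored as not having progressed.** It is not: LOCF carries the observed change, including decline. At constant SD, 100 - 39.3 = 60.7% of declining Month 4 dropouts are still scored as worse.
- **The two missing-data rules contradict each other.** Treating inability as failure and other withdrawal as missing data is coherent. What is missing is precedence when both apply to one subject.
- **LOCF favours RT001 because gastrointestinal intolerance will drive dropout.** Both withdrawals in RT001-002 were on RT001 (Section 6.4), so unequal dropout is possible. But placebo is also an oil capsule, no dropout rate by arm is given, and subjects who leave during the loading month have no Day 120 value to carry. On the design assumption that active improves, LOCF works against RT001.

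**Conclusion.** The concern holds as a method weakness of low to moderate severity. The carried value is normally a Day 120 or Day 240 result, and it misstates Month 11 response wherever subjects change. The error flatters a declining arm and penalises an improving one, so the documents support no single direction for the between-arm bias: about +2.5 points for active if both arms decline equally with 20% v 5% dropout, but a fall in the difference from 52.3 to 45.9 points if the design assumptions hold with 20% dropout in both arms.

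The move from 22.7% to 39.3% is the largest of the modelled shifts for a single declining subject at the zero threshold. It should not be read as a shift in an arm's rate, which is about 2 to 5 points for placebo. All sizes rest on linear change, the Month 11 reading of the peak workload figures, the SD pattern and assumed dropout.

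Two features could enlarge the problem but cannot be sized from the document. One is early placebo response: Section 6.4 reports "a decrease of 2.8 FARS points in the placebo group" by Day 28 in RT001-002, which LOCF would preserve if it lasted to the carried visit. The other is the population. If ITT rather than mITT were used, a carried baseline would score as stable.

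**What to change.** Replace the LOCF sentence in Section 14.1, and carry the change into the statistical analysis plan before unblinding:

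1. Impute the missing Month 11 value by multiple imputation from the planned mixed model. Derive responder status in each imputed data set and combine the results.
2. Keep death and inability to perform the test as non-response, and state that this takes precedence when such a subject also drops out.
3. Report, as a sensitivity analysis, all non-completers counted as non-responders.
4. State the analysis population, the threshold for stabilization, and whether quartile cutoffs are taken from observed data or within each imputed data set.

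Non-responder imputation should not be the main rule. On the same model it lies further from the Month 11 placebo rate of 22.7% than LOCF does: 20.5/18.2/15.9% at 10/20/30% dropout, against 24.4/26.0/27.7%. With equal decline and 20% v 5% dropout it gives (0.05 - 0.20) x 0.227 = -3.4 points for active.

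Cost: revised wording and a little more analysis work. The main analysis then relies on a missing-at-random assumption. The sensitivity analysis will show lower rates, most of all in the arm with more dropout.
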